5.1.3 Psoriasis Area and Severity Index (PASI)

PASI is a physician-performed assessment of both the extent of psoriasis on the four body areas (head, trunk, upper limbs, and lower limbs) and the degree of plaque erythema, scaling, and thickness. The PASI score accounts for both the extent of BSA affected by erythema, scaling, and thickness, and the severity of erythema, ranging from 0 (no disease) to 72 (maximal disease).

The proportion of subjects achieving PASI 75, defined as $\geq 75\%$ improvement in PASI score from baseline at the end of 8 weeks of treatment, is the secondary efficacy endpoint

Protocol Version: 00

in this study.
(See attached PASI scoring template)

5.1.4 Psoriasis Disability Index (PDI)

The Psoriasis Disability Index questionnaire was developed by Cardiff University's Dermatology Department in Wales, UK, to assess quality of life in patients with Psoriasis. It is self-explanatory and can be handed to the patient to fill in, without the need for a detailed explanation. It is usually completed in three or four minutes

Scoring (Visual Analogue Scale)

The scoring of each question is answered on a graded scale from 0 to 6. If a question is left unanswered, the score taken is 0. The PDI is calculated by summing the scores of the fifteen questions, resulting in a maximum of 90 and a minimum of 0. The higher the score, the greater the impairment of quality of life. The PDI can also be expressed as a percentage of the maximum possible score of 90.

Scoring (Tick-box method)

The scoring of each question is answered on a series of 4 answers: not at all (scores 0), a little (scores 1), a lot (scores 2), very much (scores 3). If a question is left unanswered, the score taken is 0. The PDI is calculated by summing the scores of the 15 questions, resulting in a maximum of 45 and a minimum of 0. The higher the score, the greater the impairment of quality of life. The PDI can also be expressed as a percentage of the maximum possible score of 45.

The PDI can be analyzed under five headings as follows

		VAS	Tick-Box
Daily Activities	Questions 1, 2, 3, 4, 5	Score max: 30	15
Work or School or alternative questions	Questions 6, 7, 8	Score max: 18	9
Personal relationships	Questions 9, 10	Score max: 12	6
Leisure	Questions 11, 12, 13, 14	Score max: 24	12
Treatment	Questions 15	Score max: 6	3

See attached PDI questionnaire.

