1.5.2 Toxicology

2. OBJECTIVES

- To observe the efficacy and safety of TC Cream twice daily compared to placebo over 8 weeks in subjects of the US population of patients with psoriasis vulgaris (stable stage) based on Investigator's Static Global Assessment (ISGA), Target Lesion, Psoriasis Area and Severity Index (PASI).
- To evaluate the effects and improvements of TC Cream on the quality of life in subjects with psoriasis vulgaris based on Psoriasis Disability Index (PDI) and Dermatology Life Quality Index (DLQI), and to determine whether there is further improvement or recurrence of psoriasis after the cessation of TC Cream after 8 weeks of treatment for psoriasis.
- To investigate and summarize the curative effect and recurrence rate of TC Cream on treated psoriasis patients of the US population.

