8. DATA MANAGEMENT

8.1 Fill in CRF

Protocol Version: 00

The case report form (CRF) is the primary data collection instrument for the study. All data requested on the CRF must be recorded. All missing data must be explained. If a space on the CRF is left blank because the procedure was not done or the question was not asked, write “N/D”. If the item is not applicable to the individual case, write “N/A”. All entries should be printed legibly in black ink. If any entry error has been made, to correct such an error, draw a single straight line through the incorrect entry and enter the correct data above it. All such changes must be initialed and dated. **DO NOT ERASE, OVERWRITE, OR USE CORRECTION FLUID OR TAPE ON THE ORIGINAL.**

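### Unanswered PDI items score 0, the best value, with no limit on blanks, so the score mixes completeness with disability; the bias between arms can go either way

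*Combined protocol and SAP*

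**What the plan says.** Section 5.1.4 describes two ways of scoring the PDI. On the visual analogue version, "The scoring of each question is answered on a graded scale from 0 to 6", and the total comes from "summing the scores of the fifteen questions, resulting in a maximum of 90 and a minimum of 0". The tick-box version scores each answer from 0 (no effect at all) to 3, and its total comes from "summing the scores of the 15 questions, resulting in a maximum of 45 and a minimum of 0". For each version the section adds "If a question is left unanswered, the score taken is 0" and "The higher the score, the greater the impairment of quality of life". It gives no minimum number of answered questions, no proration, and no condition under which a form is invalid.

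Section 2 gives the purpose of the measure: "To evaluate the effects and improvements of TC Cream on the quality of life in subjects with psoriasis vulgaris". The synopsis calls this a secondary objective, while section 5.1 lists the PDI itself as a tertiary endpoint. Section 8.1 says of the case report form that "All missing data must be explained". Section 9.2.3 keeps dropouts in the ITT set, and section 9.2.4 gives no method for missing data. Section 9.2.4.1 summarises measurement data by mean, standard deviation, range and a 95% confidence interval for the mean.

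**The concern.** A blank is not an answer, but the rule records it as the most favourable one. The total then reflects how completely the form was filled in as well as how much the disease interferes with life. With no cap, the rule runs to its extreme: a returned form with no answers is indistinguishable from that of a patient with no impairment.

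The PDI is one of only two instruments serving the quality-of-life objective. If completion differs by visit or by arm, the reported means, changes and confidence intervals shift for reasons unrelated to the cream. Once the data are unblinded, a new rule for blanks would be hard to defend, so it has to be set beforehand.

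**Working it through.** **1. The plan's own figures.** 15 × 6 = 90 and 15 × 3 = 45. The five subscale maxima add up: 30 + 18 + 12 + 24 + 6 = 90 and 15 + 9 + 6 + 12 + 3 = 45. The stated scoring reproduces exactly.

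**2. Effect on one patient.** Assume a patient whose true state is unchanged and whose items all have the same value. With k blanks, the scored total is the true total × (15 − k)/15.

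| Blanks after baseline | Tick-box, every item 2 (true total 30) | VAS, every item 4 (true total 60) | Apparent change |
|---|---|---|---|
| 1 | 28 | 56 | −6.7% |
| 3 | 24 | 48 | −20% |
| 5 | 20 | 40 | −33.3% |
| 15 | 0 | 0 | −100% |

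The same 3 blanks at baseline instead make the tick-box score rise from 24 to 30, a false worsening of 6 points.

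**3. Direction between arms.** Suppose a fraction m of returned forms is wholly blank. The arm mean becomes true mean × (1 − m). The tick-box means below are assumed; a negative difference (TC minus vehicle) favours TC.

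- True 15 vs 15, blank 20% TC and 5% vehicle: 12.00 − 14.25 = −2.25, a false benefit.
- True 15 vs 15, blank 5% TC and 20% vehicle: 14.25 − 12.00 = +2.25, a false harm.
- True 10 vs 15, blank 20% in both: 8 − 12 = −4.0 against a true −5, a diluted benefit.

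**4. Size between arms.** The 44 per arm comes from section 9.1. The documents give no PDI mean, SD or blank rate, so mean 12, SD 7, no true difference and the rates below are assumptions. The 5% two-sided test is a yardstick only.

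*Item skips averaging 1 vs 0.25 per form.* False difference = 12 × (1 − 0.25)/15 = 0.6 points. Standard error = 7 × √(2/44) = 1.49. The ratio is 0.6/1.49 = 0.40, so the rejection rate is Φ(−1.96 + 0.40) + Φ(−1.96 − 0.40) ≈ 0.06 + 0.01, about 7%.

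*Wholly blank returned forms, 5% vs 20%.* False difference = 12 × (0.20 − 0.05) = 1.8 points. The zeros also widen the spread. With E(X²) = 7² + 12² = 193, the variances are 0.95 × 193 − 11.4² = 53.4 and 0.80 × 193 − 9.6² = 62.2. Standard error = √((53.4 + 62.2)/44) = 1.62, the ratio is 1.11, and rejection is Φ(−0.85) + Φ(−3.07), about 20%. A simulation of 20,000 trials, with scores limited to 0–45, agrees: 20% to 21%, depending on which arm has more blanks. It gives 1.2 points and 11.6% for blank rates of 10% vs 20%, and about 5% for equal rates of 10%.

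**The case against.** The strongest reply is that the point is small. The PDI is tertiary. The t-test in section 9.2.4 is for response rates, and no PDI comparison is specified, so no stated error rate is being breached. The form has 15 questions and, by section 5.1.4, takes three or four minutes, so large numbers of wholly blank forms are unlikely and nothing in the documents suggests them. All of this stands. It limits the size but does not make the rule sound: means and confidence intervals are biased with or without a test.

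Three stronger readings are tempting, and the documents do not support them.

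- A reader might infer that missing data always count as treatment benefit. They do not: baseline blanks look like worsening, similar blank rates at both visits roughly cancel in the mean change, and more blanks on vehicle work against TC.
- A reader might infer that a dropout's uncollected form scores 0. The rule is about unanswered questions; the plan is silent on forms never completed, which is a separate gap.
- A reader might see a contradiction with section 8.1. That section governs what staff write in empty spaces, and an item can be explained there and still be scored 0.

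Nor can it be shown that the PDI and DLQI treat blanks differently. Section 5.1.5 states no such rule, but the attached questionnaires are not available and may contain one.

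There is also a fair objection to making a prorated score the main result. It would displace the rule the protocol quotes. Where an item is blank because it does not apply, proration would impute disability from unrelated questions.

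**Conclusion.** The point holds in limited form. Followed as written, section 5.1.4 lets blanks lower the score without limit and scores a returned blank form as perfect quality of life. This is a stated rule that gives a wrong result, not merely a missing detail.

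Within a patient the distortion is 1/15 of the total per blank when items are evenly scored. Between arms its direction cannot be known in advance. Its size rests on assumed values: about 0.6 points for modest differences in skipped items, and about 1.8 points in the hypothetical whole-form case. The corresponding 7% and 20% rejection rates are illustrations, because the plan names no PDI test. The practical consequence is unreliable PDI means and intervals for a tertiary endpoint; the primary endpoints are unaffected.

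**What to change.** Amend section 5.1.4 before unblinding:

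- Keep the quoted score for forms with few blanks, and add a pre-specified maximum beyond which the total is missing, for example more than 3 of 15 blank. The exact number is a judgement. At 3 blanks, the remaining distortion is at most 20% of an evenly spread score.
- State that a blank or uncompleted form is missing and never 0, and say how missing totals enter the summaries.
- Tabulate blanks by arm and visit.
- Report a prorated score (mean of answered items × 15) as a sensitivity analysis. An unchanged patient answering 2 throughout who skips 3 items would then score (24/12) × 15 = 30 rather than 24.

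The cost is a few sentences of scoring text and a little more analysis work. The downside is that a few forms lose a score.

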5.1.5 Dermatology Life Quality Index (DLQI)

The Dermatology Life Quality Index (DLQI) is the most widely used measure for assessing quality of life related to skin disease in psoriasis trials. This tool consists of 10 questions covering six domains (symptoms and feelings, daily activities, leisure, work and school, personal relationships, and trouble with psoriasis treatment). The response options range numerically from 0 to 3 points, with 0 indicating not affected at all and 3 indicating very much affected. This yields an overall score of 0–30 points, with lower scores indicating better quality of life. (See attached DLQI questionnaire.)

Table 8. Dermatology Life Quality Index (DLQI) Scale Definition

Protocol Version: 00

Score	Definition
0 to 1	No impact
2 to 5	Mild impact
6 to 10	Moderate impact
11 to 20	Very large Impact
21 to 30	Extremely large impact

5.2 Guidelines for Evaluation of Measurable Disease

All measurements should be taken and recorded in metric notation using the supplied 9x9 square ruler and camera. All baseline evaluations should be performed as close to the beginning of treatment as possible, and no more than 1 week before the beginning of treatment.

The same assessment method and technique should be used to characterize each identified and reported lesion at baseline and during follow-up.

6. SAFETY

6.1 Expected Adverse Events

In the multiple controlled randomized clinical trials conducted in China, the most frequent adverse experiences reported with TC Cream were mild skin pigmentation (mild color pigmentation, erythema); very few patients had mild chromatosis or photosensitivity. The symptoms will usually disappear with drug withdrawal. No severe adverse reactions were reported in the completed clinical studies.

6.2 Adverse Event Definition and Classification

An adverse event (AE) is defined as any untoward medical occurrence in a patient or clinical investigation subject administered a pharmaceutical product that does not necessarily have a causal relationship with the treatment. An AE can, therefore, be any unfavorable and unintended sign (including abnormal laboratory finding), symptom, or disease temporarily associated with the use of a medicinal (investigational) product, whether related to the medicinal (investigational) product.

CTCAE term (AE description) and grade: The descriptions and grading scales found in the Common Terminology Criteria for Adverse Events (CTCAE) version 4.0 will be utilized for AE reporting. All appropriate treatment areas should have access to a copy of the CTCAE version 4.0.

A copy of the CTCAE version 4.0 can be downloaded from the CTEP website.

http://ctep.cancer.gov/protocolDevelopment/electronic_applications/cTC.htm.

6.3 Serious Adverse Event

A serious adverse event (SAE) is defined as any adverse experience that results in any of the following outcomes:

- Fatal
- Life-threatening
- Requires or prolongs hospitalization
- Results in persistent or significant disability or incapacity;
- A congenital anomaly or birth defect
- An important medical event requires medical intervention to prevent one of the above outcomes.

Important medical events are those that may not be immediately life-threatening but may jeopardize the subject and may require intervention to prevent one of the other serious outcomes listed above. Examples of such events are intensive treatment in an emergency room or at home for allergic bronchospasm, blood dyscrasias, or convulsions that do not result in hospitalization. These adverse events will generally be considered serious by this criterion.

Inpatient hospitalization or prolongation of existing hospitalization means that hospital inpatient admission and/or prolongation of hospital stay were required for treatment of the AE, or that they occurred because of the event. It does not refer to pre-planned elective hospital admission for treatment of a pre-existing condition that has not significantly worsened, or to diagnostic procedures.

6.4 Laboratory and Other Safety Assessment Abnormalities Reported as AEs and SAEs

The clinical investigator will review any abnormal laboratory changes and, if any additional action is taken (e.g., reducing the dose or stopping the drug), report the laboratory abnormality as an adverse event on an Adverse Event case report form.

6.5 Pregnancy

Any pregnancy occurring during the clinical study and the outcome of the pregnancy should be recorded and followed up for congenital abnormalities or birth defects. Pregnancy tests will be performed three times using test strips at pre-study -1 (or week 0), 4, and 8. Birth control strategies should be used for age-bearing female patients.

6.6 Severity of Adverse Events

Adverse events will be classified according to the following severity scale:

- Grade 1(Mild) - The adverse event is easily tolerated and does not interfere with daily activity.
- Grade 2 (Moderate) - The adverse event interferes with daily activity, but the subject

is still able to function.

- Grade 3 (Severe) - The adverse event is incapacitating and requires medical intervention.

6.7 Relationship to Study Drug

Adverse events will be assessed for the relationship to the study drug (causality) according to the following scale:

Unrelated - The event is independent of the study drug.

Unlikely - The event may or may not follow a reasonable temporal sequence from drug administration and can plausibly be explained and/or attributed to something other than the study drug.

Possible - The event follows a reasonable temporal sequence from drug administration, follows a clinically reasonable response on withdrawal, and is unlikely to be attributed to something other than the study drug.

Probable - The event follows a reasonable temporal sequence from drug administration, follows a clinically reasonable response on withdrawal, and cannot be reasonably explained by something other than the study drug.

Definite - There is clear evidence to reveal causality, and other possible existing factors can be excluded. It follows a reasonable temporal sequence from the time of drug administration. It follows a known response pattern to the suspected drug. It disappears on cessation and recurs with reintroduction of the test drug.

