Study Design	Multi-center, randomized, double blind (Subject, Investigator), placebo controlled, parallel assignment
Study Agent /Intervention Description	
Treatment group: TC Cream: 0.3g/cm², applied to afflicted area after cleaning the skin with warm water; twice daily (morning and evening); dosage should not exceed 25g/day
 
Control group (placebo): Vehicle of TC Cream: 0.3g/cm², applied to afflicted area after cleaning the skin with warm water; twice daily (morning and evening); dosage should not exceed 25g/day

Concomitant Medications/ Therapies	None
Safety Considerations and Monitoring of adverse events	Do not expect any side effect other than mild red pigmentation which will disappear after the drug withdrawal.
Diagnosis and Main Inclusion Criteria	
 ✓ Male or female of 18-70 years old ✓ Women of childbearing age must be using birth control strategies defined by one of the following: 1) a barrier method (condom) and 2) oral contraceptives, during the 8-weeks study period. ✓ Consistent with diagnostic criteria of psoriasis vulgaris ✓ ISGA score ≥ 2 (at least mild severity) ✓ BSA (stable stage group): $1\% \leq$ to $\leq 20\%$ 
Note: Randomized, male-female ratio should be properly taken into consideration.

Main Exclusion Criteria	
 ✓ Subjects in pregnancy, preparing for pregnancy or breast feeding ✓ History of hyperergic or photosensitivity ✓ History of complicated cardiovascular disease, cerebrovascular disease, severe primary diseases in hepatic, kidney and hematopoietic system, or patients who are diagnosed with psychotic disorders ✓ Within 2/4 weeks prior to randomization the patients have taken treatment with following approved or investigational psoriasis therapy of the target lesions: 
 ○ Topical treatments ○ PUVA, UVB or Grenz ray therapy ○ Any systemic treatments other than biologicals with a possible effect on psoriasis (e.g., corticosteroids, vitamin D analogues, retinoids, hydroxycarbamide, azathioprine, methotrexate, cyclosporine, other immunosuppressants).

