3.4.2 Duration of Therapy

Subjects should continuously apply the study agent twice daily (morning and evening) for 8 weeks. 4 weeks after treatment is completed, patients are required to return for study follow-up.

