3.4.5 Early Withdrawal of Subjects

In the absence of treatment delays due to adverse events, treatment may continue until one of the following criteria applies:

- Voluntary patient withdrawal
- The investigator's decision that it is in the patient's best interest to withdraw
- If the patient becomes pregnant

Protocol Version: 00

- Noncompliance
- Significant protocol violation
- Safety reasons if any of the following occur:
 - Disease progression
 - Intercurrent illness that prevents further administration of treatment
 - Unacceptable adverse events(s)
 - Patient decides to withdraw from the study, or
 - General or specific changes in the patient's condition render the patient unacceptable for further treatment in the investigator's judgment.
- For any reason, at the Sponsor's or Investigators' discretion

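### Section 6.7: Possible, Probable and Definite all require a response on stopping the drug, so an otherwise unexplained reaction that settles during continued use fits no causality level

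*Combined protocol and SAP*

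**What the plan says.** Section 6.7 sets one scale for all adverse events: Unrelated, Unlikely, Possible, Probable, Definite.

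- Possible needs reasonable timing and that the event "follows a clinically reasonable response on withdrawal, and is unlikely to be attributed to something other than the study drug".
- Probable needs reasonable timing and that the event "follows a clinically reasonable response on withdrawal, and cannot be reasonably explained by something other than the study drug".
- Definite needs clear evidence of causality, reasonable timing, a known response pattern and exclusion of other factors. It adds: "It disappears on cessation and recurs with reintroduction of the test drug".
- Unlikely leaves timing open but needs an event that "can plausibly be explained and/or attributed to something other than the study drug".
- Unrelated needs the event to be independent of the drug.

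On exposure, Section 3.4.2 states: "Subjects should continuously apply the study agent twice daily (morning and evening) for 8 weeks". A four-week return visit follows the end of treatment. Section 3.4.5 allows for interruptions, since it opens with "In the absence of treatment delays due to adverse events". The synopsis describes the expected reaction: "Do not expect any side effect other than mild red pigmentation which will disappear after the drug withdrawal". Section 6.1 says of the reactions seen in earlier trials: "The symptoms will usually disappear with drug withdrawal".

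Section 8.3 makes a causality assessment mandatory for adverse events. Section 6.9 reports events by relationship, among other attributes. Section 9.2.4.2 limits the safety analysis to descriptive statistics.

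**The concern.** A causality scale should give every event a level, including events for which withdrawal information does not exist. Here three of the five levels depend on what happens when the drug is stopped, and the dependence is unconditional. The regimen is eight weeks of uninterrupted use, so a local reaction can appear and clear before treatment ever stops.

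For such an event the rater must still enter a level, and none is correct. A rater who holds to the withdrawal condition is left with Unlikely or Unrelated. One who overlooks it may choose Possible or Probable. With more than one center and no rule, like events may be rated differently, and the literal reading leans away from the drug. Safety is part of the primary objective (synopsis; Section 2), so the reporting by relationship should rest on definitions that can be applied.

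**Working it through.** The plan gives no figure to reproduce. The check is logical: read each definition as the set of conditions it joins with 'and', then test defined cases against it.

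**Conditions by level (Section 6.7)**

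| Level | Timing | Response on stopping | Other cause |
|---|---|---|---|
| Unrelated | not mentioned | none | event must be independent of the drug |
| Unlikely | either way | none | another plausible explanation must exist |
| Possible | reasonable | required | other cause unlikely |
| Probable | reasonable | required | no other reasonable explanation |
| Definite | reasonable | disappearance, plus recurrence on re-exposure | other factors excluded |

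The response condition appears in 3 of 5 levels. A qualifier for when it does not apply appears in 0 of 5. No sixth, unassessable level exists, and Sections 6.1, 6.8 and 6.9 do not add one.

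**Premise for all cases.** Timing is reasonable and there is no plausible other cause. Unlikely then fails because it needs another explanation. Unrelated fails because nothing shows independence from the drug. What remains turns on the response condition.

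- Case A: the event settles during uninterrupted use. There was no withdrawal to respond to, so Possible, Probable and Definite fail.
- Case B: the patient dies and the drug was not stopped beforehand. Same result.
- Case C: the drug was stopped and no response followed, including death after stopping. Read literally, all three fail. If persistence of an irreversible event counts as a clinically reasonable response, Possible and Probable are met. Definite still fails, because the event did not disappear.
- Comparison: the drug was stopped, the event responded, and there was no re-exposure. Possible and Probable are met.

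**Number of the five levels met**

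| Case | As written | Condition deleted from Possible only | Same, plus 'if the drug was stopped' in Probable |
|---|---|---|---|
| A | 0 | 1 | 2 |
| B | 0 | 1 | 2 |
| C, literal reading | 0 | 1 | 1 |
| C, persistence counts | 2 | 2 | 2 |
| Comparison | 2 | 2 | 2 |

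Deleting the condition from Possible gives every case a level and leaves the comparison case where it was. Merely excusing the condition when withdrawal information is lacking or not applicable would rescue A and B, but would leave C, read literally, at 0.

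**The case against.** The strongest reply is that the premise is narrow. A rater may take resolution despite continued twice-daily application as a sign of another cause, and psoriasis itself produces fluctuating erythema, scaling and itching, so Unlikely will often be available. That stands as a limit on how many events are caught. It does not help once no plausible alternative exists, and 6.7 has to cover that event too.

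Withdrawal information is also often available. Every completer stops at week 8 and returns four weeks later. Interruptions or earlier stops are possible (Sections 3.4.5 and 6.4), and events are followed to resolution where possible (Section 6.8). This stands for events still present when the drug stops. It does nothing for one that has already cleared.

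Stronger readings that a reader might infer are not supported:

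- *All fatal events fall outside the scale.* Only death without prior stopping is a firm case. Death after stopping belongs with case C and depends on the reading. Section 6.9, item H.1, separately asks whether a death was drug-related, although it adds no level to 6.7 and item G.4 still asks for the relationship.
- *The expected pigmentation cannot be classified.* It can, if it is still present when treatment stops and then fades.
- *Unlikely and Unrelated events will be tabulated as not drug-related.* No section groups the five levels into related and unrelated. What can be said is that the recorded level leans away from the drug.
- *Safety oversight or the trial's result is compromised.* Section 6.9 requires serious events to be reported whatever their relationship. Counts of all adverse events by arm need no causality rating, and efficacy is untouched.

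**Conclusion.** The scale is wrong as written, and the fault is minor. A well-timed event with no plausible other cause meets 0 of 5 levels if it settles under continued application, or if death occurs without the drug having been stopped. Absence of response after stopping meets 0 or 2 of 5, depending on whether persistence counts as a reasonable response.

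The conclusion assumes that the definitions are applied as worded, with 'and' joining their conditions, and that no plausible alternative cause exists. An investigator using judgement may well choose a sensible level, but 6.7 does not supply the rule for doing so. The effect is confined to the descriptive reporting of adverse events by relationship. The documents give no basis for estimating how many patients would be affected.

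**What to change.** In Section 6.7, strike the middle of the three conditions in Possible, so that it rests on two: reasonable timing after application, and no likely other cause. Leave Definite unchanged. Probable may also stay as it is. The drawback is that cases A and B then go no higher than Possible, however clear the link. If that is unwelcome, qualify the withdrawal condition in Probable with 'if the drug was stopped'.

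A sentence saying that persistence after stopping, or resolution during treatment, does not by itself make an event Unlikely or Unrelated is optional, since neither definition mentions withdrawal.

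The cost is one deleted clause, with no new data, visits or analyses. Slightly more events may be rated Possible or higher.

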6.9 Procedures for Reporting Adverse Events

Subjects will be instructed to report any adverse events that may arise during the study to clinic personnel.

All symptoms will be recorded and will be reviewed by the investigator before any subsequent drug administration.

When appropriate, medical tests and examinations will be performed to document resolution of the event(s).

Adverse events will be classified according to the MedDRA (Medical Dictionary for Protocol Version: 00

Regulatory Activities) and reported by severity, duration, relationship to the study medication(s), and action taken.

All serious adverse events occurring during the study, whether considered to be related to the study drug, will be reported to Teva within 48 hours. SAE report(s) will be typed in English.

These SAE reports will contain the following information:

- A. Study name/number
- B. Study Drug
- C. Investigator details (name, phone, fax, e-mail)
- D. Subject Number
- E. Subject Initials
- F. Subject Demographics
- G. Clinical Event
 - 1) Description
 - 2) Date of onset
 - 3) Treatment (drug, dose, dosage form)
 - 4) Relationship to study drug
 - 5) Action taken regarding the study drug
- H. If the AE was Fatal
 - 1) Cause of death (whether the death was related to the study drug)
 - 2) Autopsy findings (if available).

The notification about any serious adverse event will be directed to the Sponsor.

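### Section 6.7 grades an event that both TC Cream and psoriasis could explain as Unlikely, so drug-related counts could be understated if related means Possible or higher

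*Combined protocol and SAP*

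**What the plan says.** Section 6.7 (Relationship to Study Drug) sets out five causality grades.

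- *Unrelated*: "The event is independent of the study drug".
- *Unlikely*: "The event may or may not follow a reasonable temporal sequence from drug administration", and it "can plausibly be explained and/or attributed to something other than the study drug".
- *Possible*: the timing is reasonable, the event "follows a clinically reasonable response on withdrawal", and it "is unlikely to be attributed to something other than the study drug".
- *Probable*: the same conditions on timing and withdrawal, and the event "cannot be reasonably explained by something other than the study drug".
- *Definite*: causality is clearly shown, other factors can be excluded, and the event goes away when the drug is stopped and returns on re-exposure.

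Section 6.9 says adverse events are to be "reported by severity, duration, relationship to the study medication(s), and action taken". Section 9.2.4.2 (Safety Analyses) adds only that safety data are summarised descriptively. No section says which of the five grades count as drug-related.

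Section 6.1 names mild pigmentation and erythema as the most frequent reactions to TC Cream. The cream is applied to the affected skin (section 3.4.1). Erythema is also scored as a disease sign in section 4.3.1, in the ISGA table of section 5.1.1 and in Table 7 of section 5.1.2.

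**The concern.** The usual purpose of a middle causality grade is to hold events for which the drug is a credible cause and something else is too. Here the alternative-cause condition attached to *Possible* excludes them. A plausible second explanation is enough to send the event to *Unlikely*, whatever its timing.

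This matters for a topical product on diseased skin, because expected local reactions can resemble the disease. Redness at a treated site may be a reaction to the cream or psoriasis. The ISGA definition of score 0 even allows residual pigment change and faint redness in a lesion counted as clear. Investigators are blinded (section 3.2), so they cannot use the assignment to settle the question.

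Safety stands beside efficacy in the primary objective, and a breakdown by relationship is one of the few safety outputs the protocol specifies. At stake is whether that breakdown describes local reactions faithfully.

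**Working it through.** The documents give no figure on this point, so there is nothing to reproduce. The check is to place defined events against the five definitions.

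**Event A.** Treated-site erythema with reasonable timing that settles when the cream is stopped, and that psoriasis could plausibly explain.

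| Grade | Met? | Reason |
|---|---|---|
| Unrelated | No | Not shown to be independent of the drug |
| Unlikely | Yes | Another cause is plausible; fitting timing is no bar |
| Possible | No | Another cause is not unlikely |
| Probable | No | Psoriasis is a reasonable explanation |
| Definite | No | Other factors are not excluded |

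Only *Unlikely* fits. The event meets the timing and withdrawal conditions of *Possible* and fails on the alternative-cause condition alone.

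**Possible against Probable.** Both require reasonable timing and a response on withdrawal. They differ only between "is unlikely to be attributed to something other than the study drug" and "cannot be reasonably explained by something other than the study drug". These are nearly the same test, so two grades cover almost the same events and none covers the case where drug and disease cannot be told apart.

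**Event B.** Reasonable timing, no plausible other cause, and the subject keeps using the cream. There is no withdrawal, so the event cannot strictly meet *Possible* or *Probable*. It has no other explanation, so it does not meet *Unlikely* either. Any repair therefore has to deal with the withdrawal condition in both *Possible* and *Probable*. Removing it from one alone would leave Event B without a proper grade.

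**Effect on counts.** This depends on a grouping that the documents do not give.

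- If related means *Possible*, *Probable* or *Definite*, Event A is not counted as related.
- If related means every grade except *Unrelated*, Event A is counted and nothing is lost.
- If all five grades are tabulated with no grouping, Event A is visible under *Unlikely*.

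Under the first grouping the shift goes one way. Admitting a plausible other cause moves events from *Unlikely* up to *Possible* and moves none down. The amount needs the rate of such events in each arm and the share with a plausible other cause. The documents give neither.

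**The case against.** The strongest objection is that the undercount needs a rule the plan does not contain. A reader might infer that drug-related events are undercounted as a matter of fact. The documents do not support that: they define no related group, and under two of the three groupings above no event disappears. This stands, and the conclusion has to be conditional.

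A reader might also infer that the cream's local tolerability will look better than it is. That goes too far as well. The trial is randomised, blinded and vehicle-controlled. Section 6.9 has all symptoms recorded, and the safety set in section 9.2.3 takes in anyone randomised who used the medication even once. Counts of erythema or pigmentation by arm do not depend on the causality grade, and serious events are reported whether or not they are judged related. The same scale applies to both arms, so the vehicle arm's related count is exposed too. Nothing in the documents fixes the direction of any effect on the difference between arms. This also stands.

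Third, whether another cause is plausible or unlikely is the investigator's judgement. Section 6.1 says the expected symptoms usually disappear when the drug is withdrawn, so an investigator could reasonably judge another cause unlikely for a recognised reaction that behaves this way, and grade it *Possible*. It would therefore be wrong to say that every local reaction must be graded *Unlikely*. The definition still misplaces any event for which the investigator finds both causes credible, and erythema is a realistic instance.

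**Conclusion.** The scale is wrong as written. Read strictly, an event that both drug and disease could explain meets only *Unlikely*, and *Possible* and *Probable* barely differ. This follows from the text of section 6.7 alone and needs no assumption.

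The consequence is conditional and limited. On the assumption that drug-related means *Possible* or higher, the drug-related count could be understated in either arm. Summaries that ignore causality, and the reporting of serious events, are untouched. The size cannot be computed from the documents. The point deserves correction before enrolment because rewording is cheap then, whereas regrading collected events would be harder and, after unblinding, open to bias.

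**What to change.** Amend section 6.7 and the adverse event form as follows.

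- *Possible*: the timing is reasonable and the drug could be the cause, whether or not the disease or another cause could also explain the event. No withdrawal information is required.
- *Probable*: the timing is reasonable and another cause is unlikely (the condition now under *Possible*). Response on withdrawal is considered only where the drug was in fact stopped.
- *Unlikely*: the timing does not fit, or another cause is clearly more likely.
- *Unrelated* and *Definite* can stay as they are.

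Because the new *Possible* also contains events that meet *Probable*, add that an event takes the highest grade it meets, except that *Unlikely* applies where another cause is clearly more likely. Under these definitions Event A becomes *Possible* and Event B *Probable*.

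State in section 6.9 or 9.2.4.2 that *Possible*, *Probable* and *Definite* count as related. Alongside the breakdown by relationship, report local reactions by arm regardless of causality.

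The cost is a few sentences and a revised form. The downside is that the stated drug-related adverse event rate may be higher.
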